#### **4.8.1 Analysis of biological samples**

##### **4.8.1.1 Clinical chemistry samples**

The analyte stability limits defined by the local laboratory will be applied to all analyses performed on behalf of AstraZeneca. The local laboratory will not analyse samples that fall outside these stability limits. Analytical data will not be reported if found to have been derived from a sample that fell outside these stability limits. The standards of procedure followed by the local laboratory may be amended in accordance with its Standard Operating Procedures. The local laboratory will inform AstraZeneca of the stability limits relevant to this study before the first parent/guardian gives informed consent for his/her child to take part in the study.

## **5. DATA MANAGEMENT**

Data will be entered in the Web Based Data Capture (WBDC) system at the investigational site. The WBDC system will be authorized and approved by AstraZeneca and set up and maintained by the CRO. Trained study personnel will be responsible for entering data on the observations, tests and assessments specified in the protocol into the WBDC system and according to the eCRF Instructions within agreed timelines. The eCRF Instructions will also provide the study site with data entry instructions. Data entered in the WBDC system will be immediately saved to a central database and changes tracked to provide an audit trail. When data have been entered, reviewed, edited and Source Data Verification (SDV) has been performed, the Principal Investigator will be notified to sign a hard copy of the eCRF signature page and send it to the CRO for imaging. An electronic copy of the eCRF will be provided to the investigational site after the study database has been locked and will be archived at the investigational site.

Data checks will be run and data validation performed continuously by the CRO. The investigator should answer any queries raised by AstraZeneca or CRO during the entire duration of the study including the clean-file process.

Adverse events and Medical/Surgical history will be classified according to the terminology of the Medical Dictionary for Regulatory Activities (MedDRA). Medications will be classified according to the AstraZeneca Drug Dictionary. All coding will be performed by the CRO and reviewed and approved at AstraZeneca R&D Wilmington.

It is the responsibility of the Investigator to complete Serious Adverse Event Form when applicable. It is the AstraZeneca monitor's responsibility to ensure that any Serious Adverse Event Form is fully completed.

Data will be cleaned on a regular basis by the CRO. All decisions on the evaluability of the data from each patient must have been made and documented before the randomization codes are broken and the study is unblinded.

A minimum of data will be collected for screen failure subjects. The Data Management Plan will be written by the CRO and approved by AstraZeneca. This document will provide information on data flow, timelines and all data management activities planned for the study, including responsibilities for the personnel involved in the processes and validation procedures.

## **6. STATISTICAL METHODS AND DETERMINATION OF SAMPLE SIZE**

### **6.1 Statistical evaluation – general aspects**

A comprehensive Statistical Analysis Plan (SAP) describing the determination of the analysis populations, handling of missing data, and the calculations of the derived variables, will be prepared by Biostatistics and reviewed/approved by the study team before the unblinding of the data.

### **6.2 Description of outcome variables in relation to objectives and hypotheses**

The primary objective of this study is to evaluate if there is a difference between esomeprazole and placebo in the treatment of signs and symptoms of GERD as observed in an 8-hour video recording along with cardiorespiratory monitoring. Video, pH/impedance, and cardiorespiratory monitoring will occur at baseline (before treatment) and the final study day. Symptoms or symptomatic reflux episodes of GERD will be determined by a qualified reader, in a blinded fashion, by review of the video recording, the pH/impedance monitoring, and the cardiorespiratory monitoring. Other variables can be found in [Table 3](#).

### **6.3 Description of analysis sets**

There will be two analysis sets for the efficacy evaluation: the intent-to-treat (ITT) and the per-protocol (PP). The ITT set will include all randomized patients who take at least one dose of study medication and have valid efficacy measurements both at baseline and at the end of study. The ITT set will be considered the primary analysis set. The PP set includes all patients in the ITT set and those who do not have any major protocol violations. A detailed description of the PP population will be included in the SAP. The safety population will consist of all randomized patients taking at least one dose of study medication.

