### Study centre(s) and number of patients planned

Patients will be enrolled in the study at 3 centres located in Australia, Germany, and the United Kingdom. The study will include a minimum of 90 (to achieve 76 evaluable patients) neonatal patients, including premature and up to 1 month corrected age with symptoms of GERD (gestational age  $\geq 28$  to 44 weeks, calculated from last menstrual period or by ultrasound) admitted to a Neonatal Intensive Care Unit (NICU), special care nursery or equivalent hospital ward.

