### **3.1.4 Study Day 14 or Final Study Day**

Final study day is planned to be Day 14; however, patients who complete at least 10 days of treatment will have all final study day procedures performed. Patients who discontinue early, prior to Day 10, will need to complete all final study procedures except video/pH/impedance monitoring.

The final dose of study drug will be administered, based on the patient's body weight, per NICU standards.

A physical examination (including measurement of weight, length and head circumference), vital signs (blood pressure, heart rate, temperature, and respiration rate) and laboratory assessments will be performed.

This study day will include esophageal pH monitoring, intraluminal impedance monitoring, cardiorespiratory monitoring, and video monitoring for 8 hours. Every attempt should be made to schedule this monitoring at the same time of day as the baseline monitoring, to include at least 2 feeding times and to begin approximately 2 hours before dosing and end 6 hours after dosing). The patient will continue to be monitored for reflux only for a total of 18 – 24 hours.

A Physician Global Assessment of the patient's GERD-related symptoms over the last 24 hours will also be completed (see Section 4.6.6).

Assessment of AEs, concomitant medications, and SAEs will be completed.

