**Figure 1 Study flow chart**

**Table 1 Study summary of assessments and procedures**

Assessment/Procedure	Baseline Day -3 to Day 0	Randomization /Treatment Day 1-13	Study Completion/ Early Discontin- uation Day 14k	Safety Follow-up 14 days (+/-2 days) after final dosem
Informed consent	X			
Clinical assessment chart	X e	X e		
Medical history	X			
pH monitoring and impedance	X f		X l	
Cardiorespiratory monitoring	X		X	
Video monitoring	X f		X l	
Inclusion and exclusion criteria	X			
Vital signs a	X	X	X	X
Physical examination b	X	X i	X	X
ECG	X g			
Laboratory evaluation	X h		X	
Prior and concomitant medications	X	X	X	X
Dosing administration		X	X	
Randomization		X j		
Physician Global Assessment	X		X	
Adverse event assessment c	X	X	X	X
Serious adverse event assessment d	X	X	X	X

a Including temperature, blood pressure (BP), heart rate and respiration rate.

b Including weight, length and head circumference.

c Adverse events will be recorded from the day when the parents sign the informed consent. All ongoing AEs must be followed until resolution or until the investigator decides and documents that no further follow-up is necessary. AstraZeneca may request additional information about such AEs.

d Serious adverse events will be recorded from the day when the parents sign the informed consent.

e Baseline and final study day clinical assessment charts will be recorded during the 24 hour period before pH/impedance monitoring.

f pH/impedance/video monitoring begins once clinical assessment charts and other baseline procedures have been completed.

g Patients must have a normal ECG at baseline (historical documentation is acceptable) without clinically significant findings as deemed by the investigator.

h Stool hemocult performed at baseline only.

i Weight and length only.

j Randomization occurs on Day 1.

k Minimum of 10 days of treatment.

l Patients who discontinue early, prior to Day 10, will need to complete all final study procedures except video/pH/impedance monitoring.

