## **4. MEASUREMENTS OF STUDY VARIABLES AND DEFINITIONS OF OUTCOME VARIABLES**

### **4.1 Primary variable**

The primary variable is change from baseline in the number of occurrences of symptoms of GERD, as observed from video recording, and GERD-related signs detected from cardiorespiratory monitoring.

- For other efficacy variables, see [Table 3](#).

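### The primary set named ITT is a completers set: infants who stop before Day 10 get no final video, so they have no primary value and leave the comparison after randomisation.

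*Protocol*

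**What the plan says.** Section 6.3, repeated in the synopsis, defines the ITT set as randomised patients "who take at least one dose of study medication and have valid efficacy measurements both at baseline and at the end of study", and adds: "The ITT set will be considered the primary analysis set".

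Section 3.1.4 decides who can have the end-of-study recording. On one side, "patients who complete at least 10 days of treatment will have all final study day procedures performed". On the other, "Patients who discontinue early, prior to Day 10, will need to complete all final study procedures except video/pH/impedance monitoring". Table 1 footnote l repeats the exemption: "prior to Day 10, will need to complete all final study procedures except video/pH/impedance monitoring".

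The primary variable in Section 4.1 is "change from baseline in the number of occurrences of symptoms of GERD, as observed from video recording", together with signs from cardiorespiratory monitoring. Section 3.1.6 ties evaluability to completing the 8-hour video.

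The synopsis plans "a minimum of 90 (to achieve 76 evaluable patients". Section 6.3 describes the per-protocol set thus: "The PP set includes all patients in the ITT set and those who do not have any major protocol violations".

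**The concern.** An intent-to-treat set should be fixed by randomisation, or by randomisation and first dose, so that later events cannot decide who is compared. Here membership depends on a measurement at the end of treatment, and the visit schedule rules that measurement out for one group defined by an event after randomisation. The primary ANCOVA then compares those who stayed in each arm.

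Some reasons for stopping may be related to the counted signs. Section 3.3.5.1 lists safety reasons and development of exclusion criteria. The exclusion criteria in 3.3.3 include acute respiratory distress, which lies close to the apnea, bradycardia and desaturation that the endpoint counts. Section 3.7 says that needing an excluded medication may lead to withdrawal or make the data un-evaluable, and the excluded drugs include other reflux treatments. In the opposite direction, Section 3.1 requires infants discharged early to be readmitted for the final recording, so infants who do well may be lost too.

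If such losses differ between arms, the contrast is biased towards or away from esomeprazole, depending on which arm loses which infants.

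Separately, read literally, the per-protocol sentence is a union that contains the whole ITT set. A set of that kind removes nobody for a protocol violation.

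**Working it through.** **1. Can an early stopper be in the primary comparison?**
- Membership needs valid efficacy data at the end of study (6.3).
- The primary value needs the final video (4.1, 3.1.6).
- The final video is not made if the infant stops before Day 10 (3.1.4; Table 1 footnote l).
- Section 6.3 speaks of efficacy measurements in general, so a Physician Global Assessment at discontinuation might admit such an infant to the set on paper. The infant would still have no primary value.

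Every infant who stops before Day 10 is therefore absent from the primary analysis by design.

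**2. The plan's own figures (Section 6.5 and synopsis).** The SD is 1.5 times the difference, so the standardised effect is 1/1.5 = 0.667. Alpha is 0.05; the protocol does not state sidedness and I take it as two-sided.
- Required n per arm = 2(1.960 + 0.842)² × 1.5² = 35.3, so 36. The exact t-test gives 36.3, so 37. The stated 38 is consistent with this.
- Power at 38 per arm (t-test) = 81.8%.
- Non-evaluable allowance = 90 − 76 = 14, and 14/90 = 15.6%. Equivalently, 76/(1 − 0.15) = 89.4, so 90.

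**3. Size of a possible bias (assumptions, not in the documents).** Let a fraction *p* of one arm be lost in excess of the other, with a mean change *k* SD worse than those who remain in that arm. The full-arm mean is then (1 − *p*)·m + *p*·(m + *k*) = m + *pk*, where m is the mean of those who remain. The completers' mean misses *pk*, so the contrast shifts by *p* × *k* SD. If placebo loses the worse infants, the observed effect shrinks to 0.667 − *pk*. If esomeprazole loses them and there is no true effect, a spurious benefit of *pk* appears. With 38 per arm, t-test, SD held at its planned value:

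| Assumed loss | Bias (SD) | Power if placebo loses them | Type I error if esomeprazole loses them |
|---|---|---|---|
| Unrelated to outcome, or same loss and same deficit in both arms | 0 | 82% | 5% |
| 14 lost as 9 v 5 of 45 each, 1 SD worse: 4/45 × 1 | 0.09 | 70% | 7% |
| 10% excess, 1 SD worse | 0.10 | 68% | 7% |
| 20% excess, 1 SD worse | 0.20 | 52% | 14% |

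The last row taken literally on 45 per arm leaves 36 v 45 rather than 38 v 38; the results are then 54% and 14%, much the same.

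**4. Do the early-stop passages agree?** Section 3.1.4 and footnote l exempt video and pH/impedance. Section 3.3.5.2 asks for the final visit procedures after discontinuation and states no exemption. Table 1 attaches footnote l to the pH/impedance and video rows but not to the cardiorespiratory row, so half of the primary endpoint is still scheduled at early discontinuation. The three places do not match. Table 1 has no clinical assessment chart entry in the final/early-discontinuation column, whereas 3.3.5.2 asks for the charts to be completed.

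**The case against.** The strongest reply is that Section 6.1 leaves missing-data handling and the determination of analysis populations to the SAP, and Section 6.3 leaves the per-protocol detail there too. It is fair that the absence of an imputation method from the protocol is not itself a fault. But the protocol has already fixed the primary set and already left the recording unmade. An SAP that imputed early stoppers would contradict Section 6.3, and no SAP can recover a recording that was not taken.

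Three stronger readings are tempting, and the documents do not support them.
- *That treatment failures as such are removed.* Lack of efficacy is not among the stopping reasons in 3.3.5.1, which also include parental choice, incorrect enrolment, non-compliance and loss to follow-up. Antacid rescue and occasional restricted medication are allowed without stopping (3.3.4). Infants who fail but complete 10 days are recorded and stay in.
- *That the 14 infants are the early stoppers, or the most that can be lost.* The figure is an allowance for any cause of non-evaluability; it is neither a count nor a cap.
- *That a final video without the probe would simply supply the missing value.* Sections 4.6.2.1, 4.6.2.2 and 6.2 have the reader use the pH/impedance data, and some events are marked from it. A probe-free final recording set against a probe-assisted baseline would give a change score not comparable with the others.

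The per-protocol sentence is probably a drafting slip whose intent can be guessed. It still appears twice, in the synopsis and in Section 6.3.

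**Conclusion.** The defect in the set definition stands on the protocol's text and should be corrected before recruitment, because recordings not made cannot be recovered. What the documents establish is that infants who stop before Day 10 are outside the primary comparison because of a post-randomisation event, and that the label ITT is therefore wrong.

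What they do not establish is how many infants this affects, in which direction the bias would run, or how large it would be. The 52% power and 14% type I error are the unfavourable end of an assumed range, not an expectation; bias needs stopping that is both related to outcome and different between arms.

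**What to change.** 1. In Section 6.3 and the synopsis, define the primary set as all randomised, dosed infants with a valid baseline recording. Impute missing end-of-study counts by multiple imputation from arm, baseline count and the Physician Global Assessment at discontinuation, with chart data where available. Add a delta-adjusted sensitivity analysis that makes the imputed values progressively worse. The technical detail can sit in the SAP.
2. Keep the present set, renamed completers or evaluable, as a sensitivity analysis.
3. Reword the per-protocol set as those members of the ITT set who are free of major protocol violations.
4. Reconcile Section 3.1.4 and footnote l with Section 3.3.5.2 and with the cardiorespiratory row of Table 1. Whether early stoppers are recorded is for the sponsor to decide. If they are, the reading guidelines must make the final reading comparable with baseline.

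The cost is protocol and SAP wording and a little analysis work. No extra patients are needed: 45 per arm with complete data would have 87.9% power under the planned assumptions, although imputed values carry less information than observed ones, so that figure is a ceiling. Imputation rests on assumptions that cannot be tested, which the delta-adjusted and completers analyses are there to probe.

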## **6.5 Determination of sample size**

No relevant historical data on symptomatic episodes in this patient population was available for the sample size calculation. It was assumed that the standard deviation is about 1.5 times greater than the difference between treatment groups in number of symptomatic episodes.

Under the assumption, it would need 38 patients per group to provide at least 80% power at alpha of 0.05 to detect a difference between esomeprazole and placebo in change of symptomatic episodes from baseline.

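### The per-protocol definition adds non-violators to the ITT set instead of restricting the ITT set to them, so as worded it excludes no major violator (minor; probably a drafting slip)

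*Protocol*

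**What the plan says.** Section 6.3 names two efficacy sets, ITT and per-protocol (PP). The ITT set holds randomized patients who took at least one dose and "have valid efficacy measurements both at baseline and at the end of study". It is the main set: "The ITT set will be considered the primary analysis set".

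The PP set is defined in one sentence: "The PP set includes all patients in the ITT set and those who do not have any major protocol violations". The synopsis carries the same sentence under Statistical methods. Section 6.3 then adds: "A detailed description of the PP population will be included in the SAP". The synopsis has no such deferral. Section 6.1 also leaves the determination of the analysis populations to the SAP, to be approved before unblinding.

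Sections 6.4 and 6.5 do not mention the PP set. No endpoint, test or power figure is tied to it.

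**The concern.** A per-protocol set is normally the part of the ITT set that remains after major violators are taken out. Comparing the two results then gives some indication of whether departures from the protocol influenced the estimate. The sentence here does not take anyone out. It admits the whole ITT set and then joins a second group to it.

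PP is the only efficacy set planned besides ITT. If it were built as worded, its result for the primary variable would agree with the ITT result by construction, and a reader of the study report could mistake that agreement for evidence of robustness.

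**Working it through.** **Step 1. Set logic.** Let R be the randomized patients, I the ITT set and V the patients with a major violation.

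- I requires randomization, at least one dose, and valid baseline and end-of-study measurements. Violation status is not a condition, so I may contain members of V.
- PP as worded: I ∪ (R \\ V). This contains all of I.
- PP as evidently intended: I \\ V. This is contained in I.

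| Patient | PP as worded | PP as intended |
|---|---|---|
| In ITT, no major violation | in | in |
| In ITT, major violation | in | out |
| Not in ITT, no major violation | in | out |
| Not in ITT, major violation | out | out |

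**Step 2. Effect on the primary variable.** The second row is the defect: violators stay. The third row does not alter the primary analysis. The primary variable is change from baseline (sections 4.1 and 6.4), so an infant without a valid measurement at both times has no change score for the ANCOVA. An infant who was never dosed would not reach the final video recording, because section 3.1.4 reserves it for patients with at least 10 days of treatment. For this variable the patients actually analysed are the same in the PP set as worded and in ITT, and so are the results.

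**Step 3. Does the sample size depend on it?** Inputs from section 6.5: "the standard deviation is about 1.5 times greater than the difference between treatment groups in number of symptomatic episodes", taken as SD = 1.5 × difference; "at alpha of 0.05 to detect a difference between esomeprazole and placebo", taken as two-sided because the side is not stated; power of at least 80%.

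- Normal approximation: n = 2 × (1.960 + 0.842)² × 1.5² = 2 × 7.85 × 2.25 = 35.3, so 36 per group.
- t-test version: 36.3, so 37 per group.
- The plan says "it would need 38 patients per group to provide at least 80% power". At 38 per group, power is 82.8% (normal) or 81.8% (t-test). The stated figure stands.

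Section 6.5 does not mention the PP set, so correcting the PP sentence changes none of these figures.

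**Step 4. Size of the intended PP set.** The protocol gives no rate of major violations, so the rates below are assumptions. Start from the 76 evaluable infants in the synopsis. Intended PP size = 76 × (1 − rate), rounded. Interval width relative to ITT ≈ √(76 / PP size), assuming an unchanged SD. Power is from the t-test at effect size 1/1.5 = 0.667 with equal arms.

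| Assumed rate | PP as worded | PP as intended | Relative width | Power on intended PP |
|---|---|---|---|---|
| 5% | all 76 stay | 72 | 1.03 | 80% |
| 10% | all 76 stay | 68 | 1.06 | 77% |
| 15% | all 76 stay | 65 | 1.08 | 75% |
| 20% | all 76 stay | 61 | 1.12 | 73% |
| 30% | all 76 stay | 53 | 1.20 | 66% |

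The last column is for scale only; the protocol claims no power for a PP analysis.

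**The case against.** The strongest reply is that this is a slip of the pen. Naming two separate sets, and mentioning major violations at all, makes sense only if PP is the smaller set, and a statistician would be unlikely to build it any other way. The membership detail is left to the SAP, and sections 3.6.2 and 5 require evaluability decisions to be documented before the codes are broken. ITT is primary and no stated result rests on PP. Nearly all of this stands, and it is why the point is minor. It does not make the sentence right: a SAP that removes violators would depart from the protocol's own rule, and a SAP that follows the rule would carry the error forward.

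A reader might infer three stronger things that the documents do not support.

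- *That the trial cannot examine the effect of violations.* The SAP is not shown and may define the intended set. Only the protocol wording is shown to be wrong.
- *That up to 14 infants (90 − 76) would be added to the primary PP analysis.* Those without a valid final measurement have no change score and cannot enter it, whatever the set is called.
- *That the treatment difference is diluted by a known fraction.* This would need a violation rate, no drug effect in violators and balance between arms. The protocol gives none of these. It also permits several departures that come to mind: rescue antacid outside stated windows, occasional restricted medication, and adjusted procedures (section 3.3.4). Section 3.7 is stricter on excluded medication. Whether any of these counts as a major violation is a matter for the SAP.

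**Conclusion.** The point holds as a wording error of minor severity. As written in both places, the PP set removes no major violator, and a PP analysis of the primary variable run on it would repeat the ITT analysis. The primary analysis, the 38 per group and the stated power do not change. How many infants the correction would remove is unknown: about 4 to 23 of 76 under assumed violation rates of 5% to 30% (76 − 72 to 76 − 53), against none under the written rule. The conclusion about repetition is limited to the primary variable and to the protocol text; it says nothing about the set that the SAP finally defines.

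**What to change.** In section 6.3 and in the synopsis, replace the PP sentence with: *The PP set is the subset of ITT patients with no major protocol violation.* Make sure that the SAP's detailed description follows the corrected sentence.

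The cost is one sentence in two places. The PP set becomes smaller than ITT and its interval somewhat wider, by about 3% to 20% over the assumed range in the working. No sample size, power or primary-analysis text needs to change.
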